4.6.3.4. Special Safety Topics including Adverse Events of Special Interest

This section includes areas of interest whether due to observed safety findings, potential findings based on drug class, or safety topics anticipated to be requested by a regulatory agency for any reason. In general, potential adverse events of special interest (AESI) relevant to these special safety topics will be identified by one or more Standardized MedDRA Query(ies) (SMQs), by a Lilly-defined MedDRA PT listing based upon the review of the most current version of MedDRA, or by treatment-emergent relevant laboratory changes, as described below. Additional special safety topics may be added as warranted.

Unless otherwise specified, the special safety topics will be summarized for the Safety Population and All Lebrikizumab Safety Population during their associated study periods as described in Section 4.6.2.

Full details of the search terms and rules for deriving special safety topics in each of the sections below are described in the compound level safety standards along with information about the types of summaries and listings to be provided. In the event that the listing of terms or analysis changes for a special safety topic, it will be documented in the compound level safety standards which will supersede this document; it will not warrant an amendment to the individual study SAP.

4.6.3.4.1. Hepatic Safety

Hepatic labs include alanine aminotransferase (ALT), aspartate transaminase (AST), total bilirubin (TBL), and serum alkaline phosphatase (ALP).

Tables Related to Hepatic Safety

Analysis	Population
ALT and AST: The number and percentage of participants with a measurement greater than or equal to 3 times (3X), 5 times (5X), and 10 times (10X) the performing lab upper limit of normal (ULN) during the treatment period for all participants with a post-baseline value and for subsets based on various levels of baseline value	S, A

TBL and ALP: The number and percentage of participants with a measurement greater than or equal to 2 times (2X) the performing lab ULN during the treatment period will be summarized for all participants with a post-baseline value and for subsets based on various levels of baseline value	
Plot of maximum post-baseline ALT vs. maximum post-baseline total bilirubin	Safety Population for All Periods: ever on lebri and never on lebri

Abbreviations: A = All Lebrikizumab Safety Population; ALP = serum alkaline phosphatase; ALT = alanine aminotransferase; AST = aspartate transaminase; lebri = lebrikizumab; S = Safety Population; TBL = total bilirubin.

4.6.3.4.2. *Eosinophilia and Eosinophil-Related Disorders*

In addition to the standard laboratory analysis (Section 4.6.3.1), eosinophilia and eosinophil-related AE will be summarized. Details regarding eosinophil-related PTs are in Compound Level Safety Standard.

Tables Related to Eosinophilia and Eosinophil-Related AE

Analysis	Population
Shift table summarizing the number and percentage of participants within each maximum baseline category versus each maximum post-baseline category by treatment	S, A
Summary of eosinophil-related TEAE by PT	S, A

Abbreviations: A = All Lebrikizumab Safety Population; AE = adverse event; PT = Preferred Term; S = Safety Population; TEAE = treatment-emergent adverse event.

4.6.3.4.3. *Infections, including herpes infections, and relevant parasitic infections*

Infections will be defined using the PTs from the MedDRA Infections and Infestations System Organ Class (SOC). The MedDRA terms used to identify infections considered to be opportunistic infections (OI) in participants with immune mediated inflammatory conditions treated with immunomodulatory drugs are based on Winthrop et al. (2015) and are listed in the compound level safety standards. The list contains narrow (more specific) and broad (less specific) PTs with respect to these prospectively defined OIs. Definitions of herpes infections, parasitic infections and skin infections are listed in the compound level safety standards.

Summary Tables/Listing Related to Infection Related AE

Analysis	Population
Summary of treatment-emergent infections by maximum severity	S, A
Summary of serious infections by PT	S, A
Summary of infection AEs resulting in permanent study drug discontinuation by PT	S, A
Summary of treatment-emergent potential OI by PT nested with categories for narrow terms and broad terms separately	S, MPP, A

Summary of treatment-emergent adverse events - herpes and parasitic infections	S, A
Summary of treatment-emergent adverse events - skin infections by maximum severity	S, A
Summary and/or listing of infection follow-up form	S
A listing of participants with potential OI, serious infection, herpes and parasitic infections (including events in the Maintenance Period and the Follow-Up Period)	S

Abbreviations: A = All Lebrikizumab Safety Population; AE = adverse event; MPP = Maintenance Primary Population; OI = opportunistic infections; PT = Preferred Term; S = Safety Population; TEAE = treatment-emergent adverse event.

4.6.3.4.4. *Conjunctivitis*

Conjunctivitis are events of special interest and will be identified using PTs nested within the categories of conjunctivitis and Keratitis as described in the Compound Level Safety Standards.

Summary Tables/Listing Related to Conjunctivitis

Analysis	Population
Summary of TEAE of conjunctivitis within categories by maximum severity	S, MPP, A
Summary of TEAE of conjunctivitis cluster by maximum severity	S, MPP, A
Summary and/or listing of conjunctivitis and eye inflammation follow-up form	S
A listing of participants with conjunctivitis (including events in the Maintenance Period and the Follow-Up Period)	S

Abbreviations: A = All Lebrikizumab Safety Population; MPP = Maintenance Primary Population; S = Safety Population; TEAE = treatment-emergent adverse event.

4.6.3.4.5. *Hypersensitivity*

Potential hypersensitivity reactions will be determined using the following SMQs: anaphylactic reaction, hypersensitivity, and angioedema. Potential hypersensitivity will be categorized as immediate (i.e., occurring the same day as drug administration) and non-immediate (i.e., occurring after the day of study drug administration but prior to subsequent drug administration).

Summary Tables/Listing Related to Hypersensitivity

Analysis	Population
For immediate hypersensitivity: (1) combined narrow/algorithmic search (that is, any narrow term from any one of the SMQs, or anaphylaxis algorithm); (2) narrow search (that is, any narrow term) by SMQ; (3) broad search (that is, any narrow or broad term) by SMQ; and (4) TEAEs (occurring on the day of study drug administration) by PT not in any of the 3 SMQs	S, A
For nonimmediate hypersensitivity: (1) combined narrow search (that is, any narrow term from any one of the SMQs); (2) narrow search (that is, any narrow term) by SMQ; and (3) broad search (that is, any narrow or broad term) by SMQ	S, A

Abbreviations: A = All Lebrikizumab Safety Population; MedDRA = Medical Dictionary for Regulatory Activities; PT = Preferred Term; S = Safety Population; SMQ = Standardized MedDRA Query; TEAE = treatment-emergent adverse events.

4.6.3.4.6. *Injection Site Reactions (ISR)*

Injection site reactions (ISRs) are AEs localized to the immediate site of the administration of a drug. The evaluation of study drug related ISRs will be through the unsolicited reporting of ISR TEAEs. Injection site reactions will be defined using the MedDRA High Level Term (HLT) of Injection Site Reaction, excluding certain PTs related to joints as described in the Compound Level Safety Standards.

Tables Related to Injection Site Reactions

Analysis	Population
Summary of TEAE of ISR overall, and by PT	S, MPP, A

Abbreviations: A = All Lebrikizumab Safety Population; ISR = injection site reaction; MPP = Maintenance Primary Population; PT = Preferred Term; S = Safety Population; TEAE = treatment-emergent adverse event.

4.6.3.4.7. *Malignancies*

Malignancies will be defined using PTs from the Malignant tumors SMQ and summarized separately for the 2 categories: Non-melanoma skin cancer (NMSC) and Malignancies excluding NMSC as below.

Summary Tables Related to Malignancies

Analysis	Population
Summary of TEAE of malignancies within categories of NMSC and malignancy excluding NMSC	S, A

Abbreviations: A = All Lebrikizumab Safety Population; NMSC = non-melanoma skin cancer; TEAE = treatment-emergent adverse event; S = Safety Population.

4.6.3.4.8. *Atopic Dermatitis Exacerbation*

Atopic dermatitis exacerbation will be defined using PTs specified in the Compound Level Safety Standards and summarized below.

Summary Tables Related to Atopic Dermatitis Exacerbation

Analysis	Population
Summary of TEAE of atopic dermatitis exacerbation	S, A

Abbreviations: A = All Lebrikizumab Safety Population; S = Safety Population; TEAE = treatment-emergent adverse event.

4.6.3.4.9. *Suicide/Self-Injury*

Suicide/self-injury will be defined as described in the Compound Level Safety Standards and summarized below.

Summary Tables Related to Suicide/self-injury Standardized Medical Dictionary for Regulatory Activities Query

Analysis	Population
Summary of TEAE of Suicide/self-injury SMQ	S, A

Abbreviations: A = All Lebrikizumab Safety Population; MedDRA = Medical Dictionary for Regulatory Activities; S = Safety Population; SMQ = Standardized MedDRA Query; TEAE = treatment-emergent adverse event.

4.6.3.4.9.1. Columbia-Suicide Severity Rating Scale (C-SSRS)

The C-SSRS is an assessment tool that evaluates suicidal ideation and behavior. Information on the C-SSRS scale can be found through the following link: <http://www.cssrs.columbia.edu>.

Specifically, the following outcomes are C-SSRS categories and have binary responses (yes/no). The categories have been re-ordered from the actual scale to facilitate the definitions of the composite and comparative endpoints, and to enable clarity in the presentation of the results.

Category 1 – Wish to be Dead

Category 2 – Non-specific Active Suicidal Thoughts

Category 3 – Active Suicidal Ideation with Any Methods (Not Plan) without Intent to Act

Category 4 – Active Suicidal Ideation with Some Intent to Act, without Specific Plan

Category 5 – Active Suicidal Ideation with Specific Plan and Intent

Category 6 – Preparatory Acts or Behavior

Category 7 – Aborted Attempt

Category 8 – Interrupted Attempt

Category 9 – Actual Attempt (non-fatal)

Category 10 – Completed Suicide

Self-injurious behavior without suicidal intent is also a C-SSRS outcome (although not suicide-related) and has a binary response (yes/no).

Composite endpoints based on the above categories are defined below.

- **Suicidal ideation:** A “yes” answer at any time during treatment to any one of the five suicidal ideation questions (Categories 1-5) on the C-SSRS
- **Suicidal behavior:** A “yes” answer at any time during treatment to any one of the five suicidal behavior questions (Categories 6-10) on the C-SSRS
- **Suicidal ideation or behavior:** A “yes” answer at any time during treatment to any one of the ten suicidal ideation and behavior questions (Categories 1-10) on the C-SSRS

By-participant listings of C-SSRS and Self-Harm supplement and follow-up data will be provided (Analysis population: Safety Population). Given that few or no suicidal ideation or behaviors are anticipated, C-SSRS will be listed by participant and visit. Only participants that show suicidal ideation/behavior or self-injurious behavior without suicidal intent will be displayed (that is, if a participant’s answers are all ‘no’ for the C-SSRS, then that participant will not be displayed). However, if a participant reported any suicidal ideation/behavior or self-injurious behavior without suicidal intent at any time point then all their ideation and behavior will be displayed, even if not positive. Note, missing data should not be imputed.

The *Self-Harm Supplement Form* in the eCRF is a one-question form that is completed, at any visit, including baseline visit, that asks for the number of suicidal behaviors, possible suicidal behaviors or non-suicidal self-injurious behaviors the participant has experienced since the last assessment. For each unique event identified, a questionnaire (*Self-Harm Follow-Up Form* in the

eCRF) which collects supplemental information on the self-injurious behavior is to be completed. The Self-Harm data will be listed by participant and visit if number of events on Self-Harm Supplement Form is not zero.

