**Maintenance Period**

After completion of the Week 16 visit:

- Participants receiving 250 mg lebrikizumab Q2W
  - i. who achieve an IGA 0 or 1 and/or a  $\geq 75\%$  reduction in EASI score ( $\geq$ EASI-75) response at Week 16 will be randomly allocated to receive 250 mg lebrikizumab Q2W or 250 mg lebrikizumab Q4W, in a 1:1 fashion;
  - ii. who achieve neither an IGA 0 or 1 nor a  $< 75\%$  reduction in EASI score ( $<$ EASI-75) response at Week 16 will move to the Escape Arm.
- Participants receiving 250 mg lebrikizumab Q4W
  - i. who achieve an IGA 0 or 1 and/or an EASI-75 response ( $\geq$ EASI-75) at Week 16 will continue 250 mg lebrikizumab Q4W;
  - ii. who achieve neither an IGA 0 or 1 nor an EASI-75 response ( $<$ EASI-75) at Week 16 will move to the Escape Arm.
- Participants receiving placebo
  - i. who achieve an IGA 0 or 1 and/or an EASI-75 response ( $\geq$ EASI-75) at Week 16 will continue to receive placebo;
  - ii. who achieve neither an IGA 0 or 1 nor an EASI-75 response ( $<$ EASI-75) at Week 16 will move to the Escape Arm and will receive a loading dose of 500 mg lebrikizumab at Week 16 and Week 18.

Treatment regimen assignment will remain blinded during the Maintenance Period. Placebo injections will be utilized in order to maintain the blind and ensure that all participants receive the same number and frequency of injections regardless of treatment regimen assignment.

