4.9. Changes to Protocol-Planned Analyses

- Removed analysis for other secondary endpoint of “Number of Skin Pain-Free (Skin Pain NRS = 0) days”
- Updated definition of analysis population for the Maintenance Period

5. Sample Size Determination

Approximately 280 participants will be randomized at a 3:2:2 ratio to lebrikizumab 250 mg Q2W, lebrikizumab 250 mg Q4W, or placebo (120 participants: 80 participants: 80 participants). The inclusion of approximately 15 adolescents is based on enrollment feasibility in Japan.

The assumed IGA score of 0 or 1 at Week 16 response rates are 38% for lebrikizumab 250 mg Q2W, 33% for lebrikizumab 250 mg Q4W, and 13% for placebo. The assumed EASI-75 response rates at Week 16 are 58% for lebrikizumab 250 mg Q2W, 53% for lebrikizumab 250 mg Q4W, and 20% for placebo. The assumptions for lebrikizumab are based on the DRM06-AD01 Phase 2b study, and the proportion of participants who achieved an IGA score of 0 or 1 and proportion of participants who achieved EASI-75 response at Week 16 using the rescue medication non-response sensitivity analysis, adjusting for the allowed use of TCS. The placebo response rate is based on the review of historical TCS clinical studies in AD (Simpson et al. 2016). This study has >95% and >80% power to test the superiority of lebrikizumab 250 mg Q2W to placebo and lebrikizumab 250 mg Q4W to placebo in the co-primary endpoints based on a two-sided Fisher exact test with alpha of 0.05.

6. Supporting Documentation

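### The only planned joint ALT–bilirubin plot groups participants as ever or never on lebrikizumab over all periods, so placebo-period maxima of participants who later switch count as lebrikizumab and the placebo comparator shrinks to a small, selected remnant

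*SAP*

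**What the plan says.** SAP Section 4.6.3.4.1 (Hepatic Safety) specifies a "Plot of maximum post-baseline ALT vs. maximum post-baseline total bilirubin". Its population entry is "Safety Population for All Periods: ever on lebri and never on lebri". Each participant therefore gives one point, made of two maxima, and carries one label for the whole study.

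Three other provisions decide what that point contains:

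- **Population.** The Safety Population (SAP Section 3) is everyone randomised who received a dose in the Induction Period, so it includes the dosed placebo arm.
- **Baseline.** For safety analyses (SAP Section 4.1.1) the baseline period ends at the first Induction injection, whether placebo or active. Every later liver test is post-baseline.
- **Switching.** A placebo participant who at Week 16 shows neither of the two responses (IGA 0/1, EASI-75) "will move to the Escape Arm and will receive a loading dose of 500 mg lebrikizumab at Week 16 and Week 18" (Protocol Section 4.1, Maintenance Period). Participants rescued during Induction are also eligible for the Escape Arm. Placebo responders who lose EASI-50 between Weeks 20 and 64 switch later.

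The SAP does reset baseline for participants first exposed to lebrikizumab in the Maintenance Period, but only for treatment-emergent adverse events in the All Lebrikizumab Safety Population (Section 4.1.3). It states no such reset for this plot.

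**The concern.** Treatment changes during the study for most of the placebo arm, yet the plot treats it as a fixed attribute. As written, this has three effects.

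- A switcher's highest value can come from the placebo weeks and still be drawn as lebrikizumab.
- ALT and bilirubin maxima are taken separately. An ALT peak on placebo can therefore be paired with a bilirubin peak on lebrikizumab, giving a point that belongs to neither treatment.
- The never-exposed group is no longer the randomised placebo arm. It is mainly placebo responders who kept their response, plus early drop-outs.

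The grouping also departs from the SAP's own practice. Section 4.6.1 counts lebrikizumab exposure from the first lebrikizumab injection and leaves out placebo time in Maintenance.

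At stake is the one specified display that shows ALT and bilirubin together. Protocol Section 7.1.1 itself names that combination among its hepatic criteria. A reader of the plot could neither tell which treatment a point arose on nor judge the background rate.

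**Working it through.** **Inputs**

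- Allocation 120/80/80 (SAP Section 5).
- Placebo planning rates: EASI-75, "53% for lebrikizumab 250 mg Q4W, and 20% for placebo"; IGA 0/1, "33% for lebrikizumab 250 mg Q4W, and 13% for placebo".
- Either response keeps a placebo participant on placebo at Week 16 (Protocol Section 4.1).
- Post-baseline chemistry at Weeks 4, 8, 12, 16, 20, 28, 36, 44, 52, 60 and 68 (Protocol Section 1.3).
- Dropout and later-escape rates are not given. The ranges used below are assumptions.

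**Step 1. Reproduce the plan's figure.** The same planning rates support the claim "This study has >95% and >80% power to test the superiority", based on a "two-sided Fisher exact test with alpha of 0.05". Exact enumeration gives:

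- Q2W against placebo: 97.95% (IGA), 99.98% (EASI-75), about 97.9% for both.
- Q4W against placebo: 82.5% and 99.1%, and 81.6–81.8% for both.

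The claim reproduces. The documents give no figure for the share of placebo participants who switch, so that has to be derived.

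**Step 2. Switching at Week 16, before dropout.** Let u be the probability that a placebo participant has either response. Switchers = 80 × (1 − u); never = 80 × u; ever = 200 + switchers.

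| Overlap of the two responses | u | Switch | Never | Ever |
|---|---|---|---|---|
| IGA 0/1 nested in EASI-75 | 0.20 | 64 (80%) | 16 | 264 |
| Independent | 0.20 + 0.13 − 0.20 × 0.13 = 0.304 | 55.7 (69.6%) | 24.3 | 255.7 |
| Disjoint | 0.20 + 0.13 = 0.33 | 53.6 (67%) | 26.4 | 253.6 |

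Former placebo participants make up 53.6/253.6 = 21% to 64/264 = 24% of the ever group.

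**Step 3. Dropout and later escape.** With dropout d before Week 16 and later escape f among placebo responders, the switch share is (1 − d) × (1 − u + u × f).

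- d = 5–15%, f = 0: from 0.85 × 0.67 = 57% to 0.95 × 0.80 = 76%.
- d = 0, f = 10–30%: from 0.67 + 0.33 × 0.10 = 70% to 0.80 + 0.20 × 0.30 = 86%.

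**Step 4. What the comparator can show.** With zero cases in n participants, the one-sided 95% upper bound on the rate is 1 − 0.05^(1/n).

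- n = 80: 3.7%
- n = 26: 10.9%
- n = 16: 17.1%

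**Step 5. How often a placebo value could be the maximum.** For a Week 16 switcher, Weeks 4, 8, 12 and 16 fall on placebo if the Week 16 sample is drawn before dosing. That is 4 of 11 scheduled draws (36%), or 4 of 9 (44%) at the Week 52 lock. If peaks fell evenly over draws (an assumption), the share of the whole placebo arm with a misplaced maximum, per analyte, would run from 0.67 × 4/11 = 24% to 0.80 × 4/9 = 36%.

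**The case against.** The strongest objections, and what stands of each:

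- **Switching is not the same as misplacing a peak.** A reader might infer that the liver peaks of about 80% of the placebo arm would be plotted as lebrikizumab. The documents do not support that. The 80% is the top of the Week 16 planning range for people who switch, and a placebo value is plotted only if it exceeds every later on-drug value (Step 5). This stands in full.
- **Switching may depend on liver results.** Applying the switch share to an assumed number of ALT cases treats the two as unrelated. Protocol Section 7.1.1 asks the investigator to consider stopping study intervention for marked elevations, including raised ALT or AST with raised bilirubin. A placebo participant stopped on that ground would remain in the never group. No count of misplaced cases can therefore be derived. The loss of the comparator is unaffected.
- **The window may be defined elsewhere.** SAP Sections 4.1.3 and 4.6.3.4 refer to the compound level safety standards, which are not available here and might start post-baseline at the first lebrikizumab dose. That is possible, and it limits certainty about the misplaced maxima. It would not repair the never group.
- **Randomised liver comparisons remain.** The threshold tables in Section 4.6.3.4.1 and the laboratory scatter plots in Section 4.6.3.1 are produced for the Safety Population over Induction. To say that the plan has lost its randomised hepatic comparison would be wrong. Those displays take one analyte at a time, however.
- **The error runs against the drug.** Drawing placebo cases as lebrikizumab hides no lebrikizumab case. That is so, but a true excess also cannot be judged against a comparator of 16–26 selected participants.

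**Conclusion.** The point holds for this plot. Read as written, it assigns switchers' placebo-period maxima to lebrikizumab, allows mixed-treatment points, and replaces a randomised placebo arm of 80 with roughly 16–26 selected participants against 254–264. The upper bound with no cases rises from 3.7% to 11–17%.

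The sizes rest on the plan's placebo response rates and on the unknown overlap of the two responses, before dropout. Dropout lowers the switch share and later escape raises it. Over the assumed ranges in Step 3 it stays between 57% and 86%, so the conclusion does not depend on the exact value.

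The power statement and the single-analyte hepatic outputs are not affected.

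**What to change.** In SAP Section 4.6.3.4.1, replace the ever/never grouping with two plots:

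1. An Induction Period plot by randomised arm, with about 80 placebo and 200 lebrikizumab participants.
2. An all-period plot by treatment at the time of the test. Placebo maxima use post-baseline tests before the first lebrikizumab dose; lebrikizumab maxima use tests after it. ALT and bilirubin maxima are then always paired within one treatment.

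State the window in the SAP itself, including that a Week 16 sample drawn before the first lebrikizumab dose belongs to placebo, rather than leaving it to the compound level standard.

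The cost is minor programming on data already collected, with no change to study conduct. In the all-period plot, switchers contribute one point to each group, which a footnote should say. That plot is not a randomised comparison; the Induction plot serves that purpose.
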